Grade 3 or 4	
For Grade 3 or 4: Permanently discontinue study drug/study regimen
	
For Grade 3 or 4:
 
 - Manage severe infusion-related reactions per institutional standards appropriate clinical practice guidelines, and society guidelines (e.g., IM epinephrine, followed by IV diphenhydramine and famotidine, and IV glucocorticoid)

Non-immune Mediated Reactions		
Severity Grade of the Event (NCI CTCAE version 4.03)	Dose Modification	Toxicity Management
Any Grade	Note: dose modifications are not required for adverse events not deemed to be related to study treatment (i.e. events due to underlying disease) or for laboratory abnormalities not deemed to be clinically significant.	Treat accordingly, as per institutional standard
Grade 1	No dose modifications	Treat accordingly, as per institutional standard
Grade 2	Hold study drug/study regimen until resolution to \leq Grade 1 or baseline	Treat accordingly, as per institutional standard
Grade 3	Hold study drug/study regimen until resolution to \leq Grade 1 or baseline For AEs that downgrade to \leq Grade 2 within 7 days or resolve to \leq Grade 1 or baseline within 14 days, resume study drug/study regimen administration. Otherwise, discontinue study drug/study regimen	Treat accordingly, as per institutional standard
Grade 4	Discontinue Study drug/study regimen (Note for Grade 4 labs, decision to discontinue would be based on accompanying clinical signs/symptoms, the Investigator's clinical judgment and consultation with the Sponsor)	Treat accordingly, as per institutional standard

^a ASCO Educational Book 2015 "Managing Immune Checkpoint Blocking Antibody Side Effects" by Michael Postow MD.

^b FDA Liver Guidance Document 2009 Guidance for Industry: Drug Induced Liver Injury – Premarketing Clinical Evaluation.

AChE Acetylcholine esterase; ADL Activities of daily living; AE Adverse event; ALP Alkaline phosphatase test; ALT Alanine aminotransferase; AST Aspartate aminotransferase; BUN Blood urea nitrogen; CT Computed tomography; CTCAE Common Terminology Criteria for Adverse Events; ILD Interstitial lung disease; imAEimAE Immune-mediated adverse event; IG Immunoglobulin; IV Intravenous; GI Gastrointestinal; LFT Liver function tests; LLN Lower limit of normal; MRI Magnetic resonance imaging; NCI National Cancer Institute; NCCN National Comprehensive Cancer Network; PJP *Pneumocystis jirovecii* pneumonia (formerly known as *Pneumocystis carinii* pneumonia); PO By mouth; T3 Triiodothyronine; T4 Thyroxine; TB Total bilirubin; TNF Tumor necrosis factor; TSH Thyroid-stimulating hormone; ULN Upper limit of normal.

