4. SELECTION OF PATIENTS

4.1. Inclusion Criteria

1. Histology :

- Soft-tissue sarcoma histologically confirmed. In care outside a center of the RRePS Network, a central review is necessary ([name] team),
- histologically confirmed ovarian carcinoma (carcinosarcoma included) without known g/s BRCA mutation,

2. Ovarian carcinoma must have received at least one line of platinum-containing regimen.

3. Metastatic or unresectable locally advanced disease, not amenable to curative therapy,

4. Age \geq 18 years,

5. Eastern Cooperative Oncology Group (ECOG) performance status (PS) \leq 1,

6. Life expectancy $>$ 3 months,

7. Patients must have measurable disease (lesion in previously irradiated field can be considered as measurable if progressive at inclusion according to RECIST v1.1) defined as per RECIST v1.1 with at least one lesion that can be measured in at least one dimension (longest diameter to be recorded) as \geq 10 mm with spiral CT scan,

8. Documented disease progression according to RECIST v1.1 before study entry,

9. Patient must comply with the collection of tumor biopsies,

10. At least 1 line of chemotherapy in the palliative setting, with use of anthracyclines (for STS),

11. At least three weeks since last chemotherapy, immunotherapy or any other pharmacological treatment for neoplastic disease and/or radiotherapy,

12. Adequate hematological, renal, metabolic and hepatic function:

a. Hemoglobin \geq 9 g/dl (patients may have received prior red blood cell [RBC] transfusion, if clinically indicated); absolute neutrophil count (ANC) \geq 1.5 \times 10⁹/l, and platelet count \geq 100 \times 10⁹/l.

b. Alanine aminotransferase (ALT), aspartate aminotransferase (AST) \leq 2.5 \times upper limit of normality (ULN) and alkaline phosphatase (AP) \leq 2.5 \times ULN

c. Total bilirubin \leq ULN

d. Albumin \geq 25 g/l

e. Calculated creatinine clearance (CrCl) $>$ 60 ml/min (according to Cockcroft Gault formula).

- f. Thyroid function within normal laboratory ranges (TSH, free T3, free T4)
- g. Creatine PhosphoKinase (CPK) $\leq 2.5 \times$ ULN.

13. Women of childbearing potential must have a negative serum pregnancy test within 72 hours prior to receiving the first dose of trial medication. Both women and men must agree to use a highly effective method of contraception throughout the treatment period and for six months after discontinuation of treatment. Acceptable methods of contraception are described in protocol section 7.5,

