7.2.1. Assessing Objective Tumor Response (RECIST v1.1)

- A comprehensive workup will be performed at baseline and every six weeks.
- Whenever the response criteria are met, the appropriate imaging tests will be repeated at least four weeks later in order to confirm the response.
- The same method will be used to evaluate each identified lesion both at baseline and throughout the study.
- Treatment will be administered as long as no disease progression or unacceptable toxicity is found, or as long as no other reasons for treatment discontinuation are met.
- Assessment of efficacy will be essentially based on a set of measurable lesions identified at baseline as target lesions and followed until disease progression and following the RECIST v1.1 criteria (Eisenhauer, 2009).

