9.2.2. Phase I (Expansion cohorts)

- Eligible population: All patients included without major violation of eligibility criteria.

- Population assessable for efficacy: All patients eligible and for whom the following conditions are satisfied:
 - Received at least one complete or two incomplete treatment cycles,
 - At least one disease measurement recorded not less than six weeks after treatment onset.
- The following patients will also be included in the population assessable for efficacy; they will be considered as "inevaluable for response" for the primary endpoint as per RECIST v1.1 criteria (i.e. objective response under treatment) and not be replaced in the primary efficacy analysis:
 - Any eligible patients who received at least one treatment cycle or two incomplete treatment cycles and experience disease progression or die due to disease progression prior to response evaluation (will be considered as "inevaluable for response" due to early progression).
 - Patients withdrawn due to drug-related toxicity without any tumor assessments after the start of study treatment (will be considered as "inevaluable for response" due to toxicity).
 - Patients who received at least one administration of the treatment AND withdrawn due to significant clinical deterioration of unknown reason AND without any tumor assessments after the start of study treatment (will be considered as "inevaluable for response" due to significant clinical deterioration).
- Safety population: all patients having received at least one (any) treatment administration.

Patient's replacement:

- Any patient not eligible or not assessable for efficacy will be replaced.
- However, any patient who received at least one administration of the study drug will be included in the safety analysis.

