9.3.2.2. EXPANSION COHORTS

- All analyses will be descriptive; no p-values will be calculated.
- Analyses will be conducted separately for sarcoma and ovarian cancer patients.
- Primary efficacy endpoint will be analysed based on the eligible and assessable population (see [chapter 10.2](#) for definition):
 - Each patient will be assigned one of the following categories:
 - Complete response
 - Partial response
 - Stable disease
 - Progression
 - Inevaluable for response
 - The rate of objective response (complete or partial response) under treatment will be reported:
 - All eligible and assessable patients ([section 10.2](#)) will be included in the denominator for the calculation of the objective response rate (ORR).
 - The 95% two-sided confidence limits will be provided for the ORR (binomial law).
 - First endpoint conclusions will be based on the objective response rate ORR for all eligible and assessable patients ([section 10.2](#)) after centralized radiological review of the data.
- As regards to the other efficacy endpoints, the analyses will be carried out in the eligible and assessable population:
 - Each patient will be assigned one of the following categories:
 - Complete response
 - Partial response
 - Stable disease
 - Progression
 - Inevaluable for response
 - The rate of best overall response will be calculated as the number of patients alive with the best response (recorded from the start of the treatment) divided by the number of patients eligible and assessable ([section 10.2](#)).
 - The 6-month progression-free rate will be calculated as the number of patients remaining alive and progression-free at 6 months from the start of the treatment divided by the number of patients eligible and assessable ([section 10.2](#)).
 - The 6-month objective response rate will be calculated as the number of patients alive with complete or partial response at 6 months divided by the number of patients eligible and assessable ([section 10.2](#)).
 - The 95% two-sided confidence limits will be provided for the calculated rates (binomial law)
- The safety analysis will be performed on the safety population.
- Quantitative variables will be described using mean and standard deviations if the normality assumption is satisfied, else other descriptive statistics (median, range, quartiles) will be reported.
- Qualitative variables will be described using frequency, percentage and 95% confidence interval (binomial law).

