APPENDIX 3: EVALUATION OF RESPONSE. THE RECIST

Response and progression will be evaluated in this study using the new international criteria proposed by the revised Response Evaluation Criteria in Solid Tumors (RECIST) guideline (version 1.1) [Eur J Ca 45:228-247, 2009]. Changes in only the largest diameter (unidimensional measurement) of the tumor lesions are used in the RECIST criteria.

DEFINITIONS

Evaluable for toxicity: All patients will be evaluable for toxicity from the time of their first treatment with study drugs.

Evaluable for objective response: Only those patients who have measurable disease present at baseline, have received at least one cycle of therapy, and have had their disease re-evaluated will be considered evaluable for response. These patients will have their response classified according to the definitions stated below. (Note: Patients who exhibit objective disease progression prior to the end of cycle 1 will also be considered evaluable.)

DISEASE PARAMETERS

Measurable disease. Measurable lesions are defined as those that can be accurately measured in at least one dimension (longest diameter to be recorded) as ≥ 20 mm by chest x-ray, as ≥ 10 mm with CT scan, or ≥ 10 mm with calipers by clinical exam. All tumor measurements must be recorded in millimeters (or decimal fractions of centimeters).

Note: Tumor lesions that are situated in a previously irradiated area are not considered measurable.

Malignant lymph nodes. To be considered pathologically enlarged and measurable, a lymph node must be >15 mm in short axis when assessed by CT scan (CT scan slice thickness recommended to be no greater than 5 mm). At baseline and in follow-up, only the short axis will be measured and followed.

Non-measurable disease. All other lesions (or sites of disease), including small lesions (longest diameter <10 mm or pathological lymph nodes with ≥ 10 to <15 mm short axis), are considered non-measurable disease. Bone lesions, leptomeningeal disease, ascites, pleural/pericardial effusions, lymphangitis cutis/pulmonitis, inflammatory breast disease, and abdominal masses (not followed by CT or MRI), are considered as non-measurable.

Note: Cystic lesions that meet the criteria for radiographically defined simple cysts should not be considered as malignant lesions (neither measurable nor non-measurable) since they are, by definition, simple cysts.

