'Cystic lesions' thought to represent cystic metastases can be considered as measurable lesions, if they meet the definition of measurability described above. However, if non-cystic lesions are present in the same patient, these are preferred for selection as target lesions.

Target lesions. All measurable lesions up to a maximum of 2 lesions per organ and 5 lesions in total, representative of all involved organs, should be identified as **target lesions** and recorded and measured at baseline. Target lesions should be selected on the basis of their size (lesions with the longest diameter), be representative of all involved organs, but in addition should be those that lend themselves to reproducible repeated measurements. It may be the case that, on occasion, the largest lesion does not lend itself to reproducible measurement in which circumstance the next largest lesion which can be measured reproducibly should be selected. A sum of the diameters (longest for non-nodal lesions, short axis for nodal lesions) for all target lesions will be calculated and reported as the baseline sum diameters. If lymph nodes are to be included in the sum, then only the short axis is added into the sum. The baseline sum diameters will be used as reference to further characterize any objective tumor regression in the measurable dimension of the disease.

Non-target lesions. All other lesions (or sites of disease) including any measurable lesions over and above the 5 target lesions should be identified as **non-target lesions** and should also be recorded at baseline. Measurements of these lesions are not required, but the presence, absence, or in rare cases unequivocal progression of each should be noted throughout follow-up.

METHODS FOR EVALUATION OF MEASURABLE DISEASE

All measurements should be taken and recorded in metric notation using a ruler or calipers. All baseline evaluations should be performed as closely as possible to the beginning of treatment and never more than 4 weeks before the beginning of the treatment.

The same method of assessment and the same technique should be used to characterize each identified and reported lesion at baseline and during follow-up. Imaging-based evaluation is preferred to evaluation by clinical examination unless the lesion(s) being followed cannot be imaged but are assessable by clinical exam.

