Conventional CT and MRI: This guideline has defined measurability of lesions on CT scan based on the assumption that CT slice thickness is 5 mm or less. If CT scans have slice thickness greater than 5 mm, the minimum size for a measurable lesion should be twice the slice thickness. MRI is also acceptable in certain situations (e.g. for body scans).

RESPONSE CRITERIA

Evaluation of Target Lesions

Complete Response (CR): Disappearance of all target lesions. Any pathological lymph nodes (whether target or non-target) must have reduction in short axis to <10 mm.

Partial Response (PR): At least a 30% decrease in the sum of the diameters of target lesions, taking as reference the baseline sum diameters.

Progressive Disease (PD): At least a 20% increase in the sum of the diameters of target lesions, taking as reference the smallest sum on study (this includes the baseline sum if that is the smallest on study). In addition to the relative increase of 20%, the sum must also demonstrate an absolute increase of at least 5 mm. (Note: the appearance of one or more new lesions is also considered progressions).

Stable Disease (SD): Neither sufficient shrinkage to qualify for PR nor sufficient increase to qualify for PD, taking as reference the smallest sum diameters while on study

Evaluation of Non-Target Lesions

Complete Response (CR): Disappearance of all non-target lesions and normalization of tumor marker level. All lymph nodes must be non-pathological in size (<10 mm short axis)

Note: If tumor markers are initially above the upper normal limit, they must normalize for a patient to be considered in complete clinical response.

Non-CR/Non-PD: Persistence of one or more non-target lesion(s) and/or maintenance of tumor marker level above the normal limits

Progressive Disease (PD): Appearance of one or more new lesions and/or unequivocal progression of existing non-target lesions.

Although a clear progression of "non-target" lesions only is exceptional, the opinion of the treating physician should prevail in such circumstances, and the progression status should be confirmed at a later time by the review panel (or Principal Investigator).

Definition of the Best Response

The best response determination in trial where confirmation of complete or partial response is required:

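### A progressive lesion in an irradiated field counts as measurable for eligibility but not for response, so an eligible patient can have no target lesion for the primary endpoint

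*Protocol*

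**What the plan says.** **Eligibility.** Inclusion criterion 7, in the Protocol synopsis and section 4.1 and again in the SAP synopsis and section 2.2.2, asks for at least one measurable lesion of 10 mm or more. It adds that a "lesion in previously irradiated field can be considered as measurable if progressive at inclusion according to RECIST v1.1".

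**Response.** Section 8.1 defines objective response for the expansion cohorts by reference to Appendix 3. A note there states: "Tumor lesions that are situated in a previously irradiated area are not considered measurable". It gives no exception for progression.

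**Target lesions and partial response.** Section 7.2.1 rests the efficacy assessment on "a set of measurable lesions identified at baseline as target lesions". Appendix 3 draws target lesions from "All measurable lesions up to a maximum of 2 lesions per organ and 5 lesions in total", and a partial response requires "At least a 30% decrease in the sum of the diameters of target lesions".

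**Who counts.** Appendix 3 treats as evaluable for response "Only those patients who have measurable disease present at baseline, have received at least one cycle of therapy, and have had their disease re-evaluated". Section 9.2.2 instead asks that the patient be eligible, be sufficiently treated and have "At least one disease measurement recorded not less than six weeks after treatment onset"; it does not mention a target lesion. Section 9.3.2.2 puts every eligible and assessable patient in the ORR denominator. Section 7.2.2.1 says that the central expert's reading is the one used in the analysis.

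**The concern.** The two measurability rules give opposite answers for the same lesion. Both are current text, both appeal to RECIST v1.1, and neither document says which prevails. The difference reaches the primary endpoint, because measurability decides which lesions may be targets and the target sum decides whether a partial response can be scored. The expansion decision turns on a single response: one CR or PR in a cohort makes the combination worthy of further testing in that indication. A patient who is counted but cannot be scored as a partial response lowers the chance of passing that rule, for a reason unrelated to the treatment.

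**Working it through.** **Step 1. Follow one patient through the text.** Take an eligible patient whose only lesion of at least 10 mm lies in an irradiated field and is progressing.

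- Criterion 7: measurable, so the patient may be enrolled.
- SAP 2.2.2 check: passes if the criterion is ticked, the lesion count is above zero and any recorded lesion is at least 10 mm. No variable records an irradiated field, and the baseline listing in SAP 4.2.2 does not show one.
- Appendix 3 note: not measurable, so there is no target lesion, no baseline sum, and no way to show a 30% decrease. PR is unavailable.
- Appendix 3 evaluability: not evaluable, since measurable disease at baseline is required.
- Protocol 9.2.2 and SAP 2.4: still assessable. The SAP asks only for a completed and dated week-6 assessment. The three ways to be inevaluable for response (early progression, toxicity, clinical deterioration) do not cover this case.
- Protocol 9.3.2.2: in the denominator.

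**Step 2. The case of several lesions.** Let the baseline sum be S with the irradiated lesion included, and let that lesion measure r. PR needs a follow-up sum of at most 0.70 × S if the lesion is a target. If it is not, PR needs a sum of at most 0.70 × (S − r) over the remaining targets, and the irradiated lesion is followed only as non-target disease. These are different tests on different lesions, so the rule the central reader applies can affect the classification.

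**Step 3. Reproduce the plan's figure.** Inputs from Protocol 9.1.1 (Expansion cohorts): response rate 20%, error rate 5%, 14 assessable patients, decision rule of at least one response. The first-stage size is the smallest n with (1 − 0.20)^n below 0.05.

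- 0.8^13 = 0.0550, too large.
- 0.8^14 = 0.0440, sufficient.

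So n = 14, as stated.

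**Step 4. Effect of k sole-lesion patients among the 14.** The documents give no value for k, so the range is an assumption. Treat these patients as unable to be scored as responders. Then P(no response) = 0.8^(14 − k), and expected ORR = 0.20 × (14 − k)/14.

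| k | P(no response) | P(at least one) | Expected ORR |
|---|---|---|---|
| 0 | 4.4% | 95.6% | 20.0% |
| 1 | 5.5% | 94.5% | 18.6% |
| 2 | 6.9% | 93.1% | 17.1% |
| 3 | 8.6% | 91.4% | 15.7% |
| 4 | 10.7% | 89.3% | 14.3% |

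Per patient, the expected loss is 0.20 × 1/14 = 1.4 points. The largest possible loss, if that patient would have responded, is 1/14 = 7.1 points.

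**The case against.** The best case on the other side accepts that the sentences conflict and disputes what follows from it.

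- **Site against central reader.** A reader might infer that sites work from criterion 7 and the central expert from Appendix 3, so that the two reads diverge. The documents do not support this. Sections 4.6 and 4.7 send the sites' imaging to Appendix 3 as well, and section 7.2.2 names no measurability rule for the expert. Only the central read enters the ORR, so a different baseline sum at the site would not by itself change the result. The conflict is between the eligibility text and the response text, and it faces every reader.
- **Seven points per patient.** This might be read as the typical effect. It is the maximum, and applies only to a patient who would have responded. The expected loss is 1.4 points.
- **Frequency.** Section 1.1 describes radiotherapy with surgery as usual first-line sarcoma treatment, and a reader might conclude that affected patients are common. That does not follow: the trial enrols advanced, pretreated disease, and the subset is limited to patients whose sole lesion of sufficient size is irradiated and progressing. For ovarian carcinoma, section 1.2 describes surgery and chemotherapy and does not mention radiotherapy.
- **Complete response.** Appendix 3 still allows a CR through disappearance of non-target lesions, so treating these patients as certain non-responders is slightly pessimistic.
- **Replacement.** If Appendix 3's evaluability definition were applied, the patient would not be assessable and section 9.2.2 would have the patient replaced, which restores 14. But 9.2.2 and SAP 2.4 do not apply that definition, so this is a second unresolved conflict and not an answer to the first.

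These points limit the mechanism and the size. None of them removes the contradiction or says which rule applies.

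**Conclusion.** The concern holds as an internal inconsistency with a small but real effect on the primary endpoint. Taken literally, the plan admits a patient, keeps that patient in the denominator and rules out a partial response. One such patient in a cohort raises the chance of missing a 20% response rate from 4.4% to 5.5%, just above the planned 5%; two raise it to 6.9%. The expected ORR falls by about 1.4 points for each. These figures assume the Appendix 3 note is applied as written, the patient remains assessable under section 9.2.2, and no CR is scored through non-target disease. The number of such patients is unknown and could be zero. With several lesions, the effect is confined to the baseline sum in the central read, and the documents give no basis for its size or direction. The sample size of 14 is not in question.

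**What to change.** Reconcile the passages so that one measurability rule for irradiated lesions covers eligibility, target-lesion selection and central review. There are two consistent ways to do this.

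1. Add criterion 7's own exception to the Appendix 3 note: not measurable unless progressive at inclusion according to RECIST v1.1. This is the simplest route. It is one sentence, leaves eligibility unchanged, and should keep criterion 7's wording so that no new condition is introduced.
2. Remove the exception from criterion 7 wherever it appears in the Protocol and SAP. This is equally consistent, but it touches more places and narrows eligibility.

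Either way, state in section 7.2.2 that the central reader selects target lesions under the same rule. An irradiated-field flag in the baseline lesion data would let the SAP 2.2.2 check and the 4.2.2 listing show which patients the rule concerns; that costs one extra variable. The change should be made before central reads begin.
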